11.2 Analysis Populations

11.2.1 Intent-to-treat/Response-to-treatment/Evaluable population

All patients who meet eligibility criteria and receive at least 1 dose of nivolumab will be included in the main analysis of the response rate, even if there are major protocol deviations (e.g. incorrect treatment schedule or drug administration).

Conclusions are to be based on the population of all eligible patients. Subanalyses may be performed on various subsets of patients, such as those with no major protocol deviations or those who continued in the study for the entire treatment period (i.e. did not withdraw prematurely). Subanalysis will not serve as the basis for drawing conclusions concerning treatment efficacy.

11.2.2 Safety population

All patients enrolled in the study will be included in the safety analysis population and considered evaluable for toxicity and safety from the time of their first dose. Demographic and baseline characteristics for the safety population will be summarized by number and percent for categorical data (e.g. sex, race/ethnicity) and by descriptive statistics for continuous data (e.g. weight, vital signs, EKG readings, disease status).

11.3 Safety Analysis

11.3.1 *Evaluation of adverse events*

Treatment-emergent adverse events will be translated from investigator terms to MedDRA v.20.1 terminology and summarized (number and percentage of patients) for all patients who receive at least 1 dose. Adverse event summaries will be organized by body system, frequency of occurrence, intensity (i.e. severity grade), and causality or attribution. Patients who experience an adverse event more than once will be counted only once. The occurrence with the maximum severity will be used to calculate intensity.

11.3.2 *Evaluation of serious adverse events and premature withdrawals*

Adverse events deemed serious and those resulting in treatment withdrawal or death will be summarized separately. Narrative paragraphs will be generated to describe the circumstances surrounding each SAE and death.

11.3.3 *Evaluation of laboratory parameters and assays*

Selected clinical laboratory parameters will be summarized and clinically significant changes from baseline will be discussed.

11.3.4 *Extent of exposure*

Treatment exposure will be summarized for all patients, including dose administration, number of cycles, dose modifications or delays, and duration of therapy.

12. PROTECTION OF HUMAN SUBJECTS

12.1 *Ethical Considerations*

This study will be conducted in compliance with the protocol, GCP guidelines established by the International Conference on Harmonization, and the ethical standards set forth in the Declaration of Helsinki 2004 (available at: www.laakariliitto.fi/e/ethics/helsinki.html).

12.2 *Protocol Amendments*

Before starting the study, the protocol must be approved by each institution's IRB or Independent Ethics Committee (IEC). Amendments to the protocol may be made only with consent of the lead site/sponsor and principal investigator and are subject to IRB approval before instituting.

12.3 *Written Informed Consent*

Before obtaining consent, members of the study team will review the rationale for the treatment program with the patient. The discussion will review the alternatives available (including hormonal therapy, chemotherapy, or supportive care as appropriate), the potential benefits of this program, the risks and the probability of their occurrence, and the procedures to minimize these risks. Should an adverse event occur, the provisions available to ensure medical intervention will also be reviewed. Why the risks are reasonable in relation to the anticipated benefits, incentives, or costs that will or may be incurred as a result of participating in the study, as well as the efforts to maintain confidentiality, will also be discussed with the patient.

Patients will be required to sign and date (in duplicate) a statement of informed consent that meets the requirements of the Code of Federal Regulations (Federal Register Vol. 46, No. 17, January 27, 1981, part 50) and the IRB. The medical record will include a statement that written informed consent was obtained (and document the date that it was obtained) before the patient is enrolled in the study. The original signed document will become part of the patient's medical record, a copy will be forwarded to the lead site/sponsor pursuant to sponsor registration, and a copy will be sent home with each patient.

The consent form will include the following:

- The nature and objectives, potential toxicities, and benefits of the intended study.
- The length of therapy and likely follow-up required.
- Alternatives to the proposed therapy (including available standard and investigational therapies).
- The name of the investigator(s) responsible for the protocol.
- The right of the patient to accept or refuse treatment and to withdraw from participation in this study.
- Text regarding the coordinating center should be added to all institutional informed consent documents.

12.4 *Protection of Privacy*

Patients will be informed of the extent to which their confidential health information generated from this study may be used for research purposes. After this discussion, they will be asked to sign a Notice of Privacy Practice research authorization/HIPAA form. The original signed documents will become part of the patient's medical records, and each patient will receive a copy of the signed documents. The use and disclosure of protected health information will be limited to the individuals described in the research authorization form. The research authorization form must be completed by the principal investigator and approved by the IRB.

12.5 *Terminating or Modifying the Study*

Adverse event and laboratory data from this trial will be assessed by the medical monitor ([name]) on an ongoing basis. At least quarterly, data from the clinical database will be reviewed. The results of this review will be shared with all investigators either in writing or as part of a teleconference. SAEs will be reviewed as they are reported to the lead site/sponsor, and the medical monitor will make an assessment regarding the safety of continuing or modifying the study. This assessment will be shared with the investigators either in writing or as part of a teleconference as well as with BMS. Should the assessment of either the lead site/sponsor or the principal investigator be that the study should be terminated, the study will be closed to further accrual. Patients who are receiving treatment will be assessed individually by the investigator to see if it is in the patients' best interest to continue, which might be the case for a patient that is responding to the intervention. Follow-up safety assessments will be performed for all patients who are terminated from the study prematurely. Any planned data disclosures will also be discussed with BMS.

APPENDIX A: MANAGEMENT ALGORITHM FOR IMMUNO-ONCOLOGY AGENTS

These general guidelines constitute guidance to the Investigator. The guidance applies to all immuno-oncology agents and regimens.

A general principle is that differential diagnoses should be diligently evaluated according to standard medical practice. Non-inflammatory etiologies should be considered and appropriately treated.

Corticosteroids are a primary therapy for immuno-oncology drug-related adverse events. The oral equivalent of the recommended IV doses may be considered for ambulatory patients with low-grade toxicity. The lower bioavailability of oral corticosteroids should be taken into account when switching to the equivalent dose of oral corticosteroids.

[figure not shown]
For subjects expected who require more than 4 weeks of corticosteroids or other immunosuppressants to manage an adverse event, consider the following recommendations:

- Antimicrobial/antifungal prophylaxis per institutional guidelines to prevent opportunistic infections such as *Pneumocystis jiroveci* (PJP) and fungal infections.
- Early consultation with an infectious disease specialist should be considered. Depending on the presentation, consultation with a pulmonologist for bronchoscopy or a gastroenterologist for endoscopy may also be appropriate.
- In patients who develop recurrent adverse events in the setting of ongoing or prior immunosuppressant use, an opportunistic infection should be considered in the differential diagnosis.
- Consultation with a medical or surgical specialist, especially prior to an invasive diagnostic or therapeutic procedure, is recommended.

The frequency and severity of the related adverse events covered by these algorithms will depend on the immuno-oncology agent or regimen being used.

GI Adverse Event Management Algorithm

[figure not shown]
Rule out non-inflammatory causes. If non-inflammatory cause is identified, treat accordingly and continue I-O therapy. Opiates/narcotics may mask symptoms of perforation. Infliximab should not be used in cases of perforation or sepsis.

Patients on IV steroids may be switched to an equivalent dose of oral corticosteroids (e.g. prednisone) at start of tapering or earlier, once sustained clinical improvement is observed. Lower bioavailability of oral corticosteroids should be taken into account when switching to the equivalent dose of oral corticosteroids.

Renal Adverse Event Management Algorithm

[figure not shown]
Rule out non-inflammatory causes. If non-inflammatory cause, treat accordingly and continue I-O therapy

Patients on IV steroids may be switched to an equivalent dose of oral corticosteroids (e.g. prednisone) at start of tapering or earlier, once sustained clinical improvement is observed. Lower bioavailability of oral corticosteroids should be taken into account when switching to the equivalent dose of oral corticosteroids.

Pulmonary Adverse Event Management Algorithm

[figure not shown]
Rule out non-inflammatory causes. If non-inflammatory cause, treat accordingly and continue I-O therapy. Evaluate with imaging and pulmonary consultation.

Patients on IV steroids may be switched to an equivalent dose of oral corticosteroids (e.g. prednisone) at start of tapering or earlier, once sustained clinical improvement is observed. Lower bioavailability of oral corticosteroids should be taken into account when switching to the equivalent dose of oral corticosteroids.

Hepatic Adverse Event Management Algorithm

Rule out non-inflammatory causes. If non-inflammatory cause, treat accordingly and continue I-O therapy. Consider imaging for obstruction.

[figure not shown]
Patients on IV steroids may be switched to an equivalent dose of oral corticosteroids (e.g. prednisone) at start of tapering or earlier, once sustained clinical improvement is observed. Lower bioavailability of oral corticosteroids should be taken into account when switching to the equivalent dose of oral corticosteroids.

*I-O therapy may be delayed rather than discontinued if AST/ALT ≤ 8 x ULN and T.bili ≤ 5 x ULN.

**The recommended starting dose for grade 4 hepatitis is 2 mg/kg/day methylprednisolone IV.

Endocrinopathy Management Algorithm

[figure not shown]
Rule out non-inflammatory causes. If non-inflammatory cause, treat accordingly and continue I-O therapy. Consider visual field testing, endocrinology consultation, and imaging.

Patients on IV steroids may be switched to an equivalent dose of oral corticosteroids (e.g. prednisone) at start of tapering or earlier, once sustained clinical improvement is observed. Lower bioavailability of oral corticosteroids should be taken into account when switching to the equivalent dose of oral corticosteroids.

Skin Adverse Event Management Algorithm

Rule out non-inflammatory causes. If non-inflammatory cause, treat accordingly and continue I-O therapy.

[figure not shown]

Patients on IV steroids may be switched to an equivalent dose of oral corticosteroids (e.g. prednisone) at start of tapering or earlier, once sustained clinical improvement is observed. Lower bioavailability of oral corticosteroids should be taken into account when switching to the equivalent dose of oral corticosteroids.

*Refer to NCI CTCAE v4 for term-specific grading criteria.

Neurological Adverse Event Management Algorithm

Rule out non-inflammatory causes. If non-inflammatory cause, treat accordingly and continue I-O therapy.

Patients on IV steroids may be switched to an equivalent dose of oral corticosteroids (e.g. prednisone) at start of tapering or earlier, once sustained clinical improvement is observed. Lower bioavailability of oral corticosteroids should be taken into account when switching to the equivalent dose of oral corticosteroids.

APPENDIX B: PERFORMANCE STATUS CRITERIA

ECOG Performance Status Scale		Karnofsky Performance Scale	
Grade	Description	%	Description
0	Normal activity. Fully active, able to continue all predisease performance without restriction.	100	Normal, no complaints, no evidence of disease.
		90	Able to carry on normal activity, minor signs or symptoms of disease.
1	Symptoms, but ambulatory. Restricted in physically strenuous activity but ambulatory and able to carry out work of a light or sedentary nature (e.g. light housework, office work).	80	Normal activity with effort, some signs or symptoms of disease.
		70	Cares for self, unable to carry on normal activity or to do active work.
2	In bed < 50% of the time. Ambulatory and capable of all self-care but unable to carry out any work activities. Up and about more than 50% of waking hours.	60	Requires occasional assistance but is able to care for most needs.
		50	Requires considerable assistance and frequent medical care.
3	In bed > 50% of the time. Capable of only limited self-care, confined to bed or chair > 50% of waking hours.	40	Disabled, requires special care and assistance.
		30	Severely disabled, hospitalization indicated. Death not imminent.
4	100% bedridden. Completely disabled, cannot carry on any self-care, totally confined to bed or chair.	20	Very sick, hospitalization indicated. Death not imminent.
		10	Moribund, fatal processes progressing rapidly.
5	Dead.	0	Dead.

APPENDIX C: GLOSSARY OF ABBREVIATIONS AND ACRONYMS

17-AAG	17-allylamino-17-demethoxygeldanamycin
17-DMAG	17-dimethylaminoethylamino-17-demethoxygeldanamycin
2-MPPA	2-(3-mercaptopropyl) Pentanedioic acid
AdEERS	Adverse Event Expedited Reporting System
ADR	Adverse drug reaction
ADT	Androgen-deprivation therapy
AE	Adverse event
AGA	Androgenetic alopecia
AI	Accumulation index
ALT	Alanine aminotransferase
AML	Acute myeloid leukemia
ANC	Absolute neutrophil count
ANOVA	Analysis of variance
APTT	Activated partial thromboplastin time
AR	Androgen receptor
ASAEL	Agent Specific Adverse Event List
AST	Aspartate aminotransferase
AUC	Area under the plasma concentration-time curve
AUC(INF)	Area under the concentration-time curve from time zero extrapolated to infinite time
AUC(0-T)	Area under the concentration-time curve from time zero to the time of the last quantifiable concentration
AUC(TAU)	Area under the concentration-time curve in one dosing interval
AUMC(INF)	Area under the moment concentration time curve extrapolated to infinity
A-V	Atrioventricular
β-HCG	Beta-human chorionic gonadotrophin
%BE	Percent biliary excretion
bid	bis in die (twice a day)
BLQ	Below limit of quantification
BMI	Body mass index
BP	Blood pressure
BSA	Body Surface Area
BUN	Blood urea nitrogen
C	Celsius
Ca++	Calcium
caBIG	Cancer Biomedical Informatics Grid
CAEPR	Comprehensive Adverse Event and Potential Risks
CALGB	Cancer and Leukemia Group B

Nivolumab in Biochemically Recurrent dMMR Prostate Cancer
Johns Hopkins University

CBC	Complete blood count
CCC	Clinical Consortium Committee
CCD	Central Consortium Database
CDE	Common data element
CDUS	Clinical Data Update System
CFR	Code of Federal Regulations
CI	Confidence interval
Cl ⁻	Chloride
Cl _{cr}	Creatinine clearance
CLNR	Nonrenal clearance
CLR	Renal clearance
CLT	Total body clearance
CLT/F	Apparent total body clearance
Cm	Centimeter
C _{max}	Maximum plasma concentration
C _{min}	Trough observed concentration
COSTART	Coding Symbols for Thesaurus of Adverse Reaction Terms
CNS	Central nervous system
CR	Complete response
CRC	Clinical Research Center
CRDB	Clinical Research Database
CRF	Case report form
CRMIS	Clinical Research Management Information System
CRPC	Castration resistant prostate cancer
CT	Computerized tomography
CTC	Circulating tumor cell
CTCAE	Common Terminology Criteria for Adverse Events
CTEP	Cancer Therapy Evaluation Program
CTMS	Clinical Trials Monitoring Service
CTO	Clinical Trials Office
CV	Coefficient of variation
CYP	Cytochrome p-450
DCTD	Division of Cancer Treatment and Diagnosis
DEV	Deviation from the nominal value
%DEV	Percent deviation
dL	Deciliter
DHEA	Dehydroepiandrosterone
DHEA-S	Dehydroepiandrosterone sulfate
DHT	Dihydrotestosterone
DLT	Dose-limiting toxicity

Nivolumab in Biochemically Recurrent dMMR Prostate Cancer
Johns Hopkins University

DSM	Data and safety monitoring
EA	Extent of absorption
ECG	Electrocardiogram
ECOG	Eastern Cooperative Oncology Group
EDC	Electronic data capture
EEG	Electroencephalogram
EKG	Electrocardiogram
EORTC	European Organization for Research and Treatment of Cancer
ESF	Eligibility screening form
ESR	Expedited safety report
F	Bioavailability
FDA	Food and Drug Administration
FDG-PET	2-[18F]fluoro-2-deoxyglucose positron emitting tomography
FDHT	18-fluoro-dehydrotestosterone
%FE	percent fecal excretion
FISH	Fluorescence in situ hybridization
FSH	Follicle stimulating hormone
GAPDH	Glyceraldehyde-3-phosphate dehydrogenase
GC	Gas chromatography
GCP	Good clinical practice
GCPII	Glutamate carboxypeptidase II enzyme
GFR	Glomerular filtration rate
GGT	Gamma-glutamyl transferase
GnRH	Gonadotropin-releasing hormone
HAT	Histone acetyltransferases
HCO ₃ ⁻	Bicarbonate
HDAC	Histone deacetylase
HIPAA	Health Insurance Portability and Accountability Act
HIV	Human immunodeficiency virus
HL7	American National Standards Institute's Health Level Seven
HPF	High power field
HPLC	High-performance liquid chromatography
HR	Heart rate
HRPC	Hormone-refractory prostate cancer
HRT	Hormone replacement therapy
HSP90	Heat-shock protein 90
ICD	International Classification of Diseases
ICH	International Conference on Harmonization
IEC	Independent Ethics Committee
IHC	Immunochemical

Nivolumab in Biochemically Recurrent dMMR Prostate Cancer
Johns Hopkins University

IM	Intramuscular
IMSL	International Mathematical Statistical Library
IND	Investigational new drug
INR	International normalized ratio
IP	Intraperitoneal
IRB	Institutional Review Board
ITT	Intent-to-treat population
IV	Intravenous
K	Slope of the terminal phase of the log concentration-time curve
K+	Potassium
K3EDTA	Potassium ethylenediaminetetraacetic acid
KLK1	Kallikrein 1
LBD	Ligand-binding domain
LC	Liquid chromatography
LCM	Laser capture microdissection
LC-MS	Liquid chromatography/mass spectrometry
LD	Longest diameter
LDH	Lactate dehydrogenase
LLQ	Lower limit of quantitation
ln	Natural logarithm
LOCF	Last observation carried forward
LOI	Letter of intent
LPF	Low power field
MAD	Maximum administered dose
MDS	Myelodysplasia
MedDRA	Medical Dictionary for Regulatory Activities
MIC	Minimum inhibitory concentration
MMP	Matrix metalloproteinase
MRI	Magnetic resonance imaging
MRT	Mean residence time
MRT(INF)	Mean residence time adjusted for infusion time
MRT(PO)	Mean residence time following oral administration
MRT(SS)	Mean residence time at steady-state
MSKCC	Memorial Sloan-Kettering Cancer Center
MS	Mass spectrometry
MTD	Maximum tolerated dose
N	Number of subjects or observations
NA	Not applicable
N/A	Not available
NBN	National Biospecimen Network

Nivolumab in Biochemically Recurrent dMMR Prostate Cancer
Johns Hopkins University

NCI	National Cancer Institute
NIH	National Institutes of Health
NOAEL	No observed adverse effect level
NOS	Not otherwise specified
NSAID	Nonsteroidal anti-inflammatory drug
NTX	N-telopeptide cross-link
NVB	Neurovascular bundle
OCR	Office of Clinical Research at MSKCC
PCCTC	Prostate Cancer Clinical Trials Consortium
PCRP	Department of Defense Prostate Cancer Research Program
PD	Progressive disease
PET	Positron emission tomography
PFS	Progression-free survival
PI	Principal investigator
PIN	Prostatic intraepithelial neoplasia
PK	Pharmacokinetics
PMB	Pharmaceutical Management Branch
PO	per os (by mouth)
PR	Partial response
PSA	Prostate-specific antigen
PSA-DT	Prostate-specific antigen doubling time
PSMA	Prostate specific membrane antigen
PT	Prothrombin time
PTT	Partial thromboplastin time
QC	Quality control
qd	quaque die (every day)
qRT-PCR	Quantitative reverse transcription-polymerase chain reaction
QOL	Quality of life
RBC	Red blood cell
RC	Research Council
RDBMS	Relational Database Management System
RDRC	Radioactive Drug Research Committee
RECIST	Response Evaluation Criteria in Solid Tumors
RP	Radical prostatectomy
RPC	eResearch Program Coordinator
RSA	Research Study Assistant
RSD	Relative standard deviation
%RSD	Percent relative standard deviation
SAE	Serious adverse event
SAHA	Suberoylanilide hydroxamic acid

Nivolumab in Biochemically Recurrent dMMR Prostate Cancer
Johns Hopkins University

SC	Subcutaneous
SD	Standard deviation
SD	Stable disease
Seq	Sequence
SHBG	Sex hormone binding globulin
SKI	Sloan-Kettering Institute for Cancer Research
SMD	Stable metabolic disease
SOP	Standard Operating Procedures
SPORE	Specialized Programs of Research Excellence
STAR	Symptom Tracking and Reporting
SUV	Standardized uptake value
t	Temperature
t _{1/2}	Terminal half-life
T	Time
TAUC(TAU)	Trapezoidal area under the concentration-time curve in one dosing interval
TAUC(0-T)	Trapezoidal area under the concentration-time curve from time zero to the time of the last quantifiable concentration
TDP	Time to disease progression
TGP	Prostate-specific transglutaminase
tid	ter in die (3 times a day)
TMA	Tissue microarray
Tmax	Time of maximum observed concentration
TMPRSS2	Transmembrane protease, serine 2
TNM	Tissue, lymph node, metastases
TX	Treatment
ULN	Upper limit of normal
ULQ	Upper limit of quantitation
UR	Urinary recovery
VEGF	Vascular endothelial growth factor
Vss	Volume of distribution at steady-state
WBC	White blood cell
WHO	World Health Organization

APPENDIX D. ACCEPTABLE BIRTH CONTROL METHODS

Subjects with partners of childbearing potential, who are sexually active, must agree to the use of TWO highly effective forms of contraception (defined as a method that can achieve a failure rate of < 1% per year when used consistently and correctly) in combination [as listed below], throughout the period of taking study treatment and for at least 7 months after last dose of study drug(s), or they must totally/truly abstain from any form of sexual intercourse [see below].

Highly Effective Non-hormonal birth control methods include:

- Total sexual abstinence. Abstinence must continue for the total duration of study treatment and for at least 1 month after the last dose. Periodic abstinence (e.g. calendar ovulation, symptothermal post ovulation methods) and withdrawal are not acceptable methods of contraception.
- Vasectomised sexual partner PLUS male condom. With participant assurance that partner received post-vasectomy confirmation of azospermia.
- Tubal occlusion PLUS male condom.
- IUD PLUS male condom. Provided coils are copper-banded.

Highly Effective hormonal methods:

- Normal and low dose combined oral pills PLUS male condom.
- Cerazette (desogestrel) PLUS male condom. Cerazette is currently the only highly efficacious progesterone based pill.
- Hormonal shot or injection (e.g. Depo-Provera) PLUS male condom.
- Etonogestrel implants (e.g. Implanon, Norplant) PLUS male condom.
- Norelgestromin / EE transdermal system PLUS male condom.
- Intrauterine system [IUS] device (e.g. levonorgestrel releasing IUS - Mirena®) PLUS male condom.
- Intravaginal device (e.g. EE and etonogestrel) PLUS male condom.

APPENDIX E. ACTIONS REQUIRED IN CASES OF COMBINED INCREASE OF AMINOTRANSFERASE AND TOTAL BILIRUBIN – HY’S LAW

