- Male participants and their partners, who are sexually active and of childbearing potential, must agree to the use of two highly effective forms of contraception in combination (see Appendix D for acceptable methods), throughout the period of taking study treatment and for 7 months after the last dose of nivolumab to prevent pregnancy in a partner.
- No evidence (within 5 years) of prior malignancies (except successfully treated basal cell or squamous cell carcinoma of the skin).

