8.1.7 Pregnancy

Male participants should refrain from fathering a child or donating sperm during the study and for 7 months following the last dose of nivolumab.

Pregnancy of the patient's partners is not considered to be an adverse event. However, all pregnancies must be reported and submitted to BMS within 24 hours/ 1 business day of becoming aware of the event. BMS will perform due diligence follow-up using the BMS Pregnancy Form which the investigator must complete.

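### Appendix D sets a 1-month minimum for abstinence after the last dose and does not reconcile it with the 7-month pregnancy-prevention period stated elsewhere in the protocol

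*Combined protocol and SAP*

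**What the plan says.** Four statements in the protocol bear on how long pregnancy prevention lasts after treatment.

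- **Section 3.3, Inclusion Criteria.** Sexually active participants and partners of childbearing potential must agree to use two contraceptive methods together, "throughout the period of taking study treatment and for 7 months after the last dose of nivolumab to prevent pregnancy in a partner". The criterion sends the reader to Appendix D for the accepted methods.
- **Section 8.1.7, Pregnancy.** The instruction reads: "Male participants should refrain from fathering a child or donating sperm during the study and for 7 months following the last dose of nivolumab". This is addressed to male participants generally and makes no distinction by method.
- **Appendix D, opening paragraph.** Sexually active subjects with partners of childbearing potential must use two methods while they are being treated, then "for at least 7 months after last dose of study drug(s), or they must totally/truly abstain from any form of sexual intercourse", followed by a pointer to the text below.
- **Appendix D, abstinence bullet.** The first entry in the list of non-hormonal methods is "Total sexual abstinence", and its duration is given as: "Abstinence must continue for the total duration of study treatment and for at least 1 month after the last dose".

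**The concern.** Three statements give 7 months after the last dose and one gives a minimum of 1 month. The protocol offers no reason for a shorter period with abstinence and does not say what a man should do if he stops abstaining between month 1 and month 7.

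Appendix D is operative text, because the eligibility criterion refers sites to it for the accepted methods. Staff at the two sites could read the same document and give different advice. What is at stake is the safety of participants' partners. The protocol itself treats partner pregnancy as important enough to require a report to the drug supplier within 24 hours or 1 business day. No estimate or test in the analysis depends on the point.

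**Working it through.** The plan has no computed figure to reproduce. The check is a comparison of the texts and one subtraction.

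| Place | Who is addressed | What is required | Period after last dose |
|---|---|---|---|
| 3.3 | Sexually active participants and partners of childbearing potential | Two contraceptive methods | 7 months |
| 8.1.7 | All male participants | Not fathering a child, not donating sperm | 7 months |
| Appendix D, opening | Sexually active subjects with partners of childbearing potential | Two methods, or total abstinence | At least 7 months, attached to the two-method option |
| Appendix D, abstinence bullet | Men choosing abstinence | Abstinence | At least 1 month |

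**Difference in stated minimum:** 7 months − 1 month = 6 months, running from month 1 to month 7 after the last dose. This measures a difference in wording. It does not measure exposure.

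**Following one man through the text.**

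1. He chooses abstinence. The opening of Appendix D gives that as the alternative to two methods and sends him to the list below.
2. The list gives him one duration: treatment plus at least 1 month.
3. He stops abstaining at month 1. He has met the bullet as written, and Appendix D gives no instruction to switch to another listed method.
4. What happens next decides whether another section is breached:
   - If he moves to two accepted methods until month 7, he meets the contraception requirement of 3.3. He also stays within 8.1.7 provided he does not father a child or donate sperm.
   - If he has intercourse with a partner of childbearing potential without the required contraception before month 7, he falls outside 3.3.
   - If he fathers a child or donates sperm before month 7, he falls outside 8.1.7.
5. If he abstains for the full 7 months, all four statements are satisfied together.

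The four statements can therefore all be met at once, but a man or a site relying on the abstinence bullet alone is not led to the behaviour that meets them.

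**The case against.** The strongest reply is that the 7-month protection is stated and that the bullet only fails to repeat it. It has four parts.

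- **The bullet sets a floor.** It asks for at least 1 month, so longer abstinence is compatible with it. This is true, but the minimum is what a participant must meet, and stopping at month 1 meets it.
- **In the opening of Appendix D, the 7 months attaches to the two-method option.** Abstinence follows the word *or*, and its duration is left to the text below. This stands as grammar. A reader might infer that the appendix flatly contradicts itself, but that sentence can be read as setting different durations for two options. The clearer tension is with 8.1.7, which covers every male participant for 7 months.
- **A man who resumes intercourse becomes sexually active and so comes under 3.3.** This reading is available, and it means that months 1 to 7 cannot be described as having no stated protection. Appendix D does not say it, however, so the safeguard has to be inferred.
- **Ending abstinence at month 1 is not a breach.** This also stands. Section 8.1.7 does not require abstinence from intercourse, and 3.3 requires contraception only of the sexually active. A reader might infer that anyone who follows the bullet violates both sections. The documents support that only if one of the further steps shown above occurs.

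It is also fair to say that the consent pages are not available here. Whether participants are told 1 month or 7 months cannot be judged from these documents.

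**Conclusion.** Wrong as written: this is an internal inconsistency, and nothing in the protocol presents it as a deliberate choice. The 1-month minimum in the abstinence bullet is not reconciled with the 7-month period in 3.3, in 8.1.7 and for the two-method option in the opening of Appendix D. No other text resolves it.

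The stated durations differ by 6 months. A reader might infer that every man who uses abstinence is left unprotected for those 6 months. The documents do not support that, because only a man who resumes intercourse before month 7 without the required contraception is affected. How many would do so is unknown. Planned enrolment is 15 in total, and the documents do not say how many men would rely on abstinence.

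The conclusion assumes only that sites use Appendix D as 3.3 directs. It takes no view on which duration is clinically correct.

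**What to change.** Reconcile the abstinence bullet in Appendix D with the opening of that appendix, section 3.3 and section 8.1.7, so that the requirement after the last dose is consistent whichever accepted method a man uses. If different durations by method are intended, the appendix should say so, explain how that fits with 8.1.7, and state what applies to a man who stops abstaining before month 7. The clinical team must decide the duration.

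Check that the consent form and other patient-facing material agree with the reconciled text. The protocol change is about one line of wording, with no effect on sample size, endpoints or analysis.
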